3.3 SAMPLE SIZE

Based on previous clinical trials with similar assessments and participant burden (see the protocol for more details), it is estimated that a minimum of 60 participants (and up to 90) per site will be required. This will result in a total of 300-450 participants across the five clinical sites. With a sample size of 300, conservative assumptions about the impact of the propensity score weighting, and a type I error rate of 0.05, we will have 80% power to detect effect sizes that are at least as large as 0.23 for each environmental measure when they are modelled as continuous predictors. This represents the minimum change in the HD composite outcome that would be detected as statistically significant with 80% power for a 1-unit change in the

TPL/008/2(v1.0)

DOMINO-HD: STATISTICAL ANALYSIS PLAN

environmental measure, suggesting the study has reasonable power for small to moderate effects.

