4. STATISTICAL PRINCIPLES

4.1 LEVELS OF CONFIDENCE AND P-VALUES

95% confidence intervals will be reported. All p-values will be compared to 5% level of significance.

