4.1.1 ADJUSTMENT FOR MULTIPLICITY

None due to the exploratory nature of the study.

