A MET-minute is the amount of energy expended during a minute while at rest. It is a ratio of a person's working metabolic rate relative to their resting metabolic rate (one MET is the energy spent sitting at rest for one minute). As there is no evidence in the literature about a clear distinction between active and inactive lifestyle for individuals with HD, participants in the lowest tertile (\leq 33%) will be classified as inactive (Schiepers et al., 2018). MET-minutes will be extracted from FitBit. MET-minutes will be used as an alternative measure of physical activity (if available) to assess the sensitivity of our findings.

Construction of LifeHD score:

A LIBRA style index (Anstey et al., 2013; Kivipelto et al., 2006; Schiepers et al., 2018) will be created to investigate the association of a lifestyle-based score with the progression of HD

TPL/008/2(v1.0)

DOMINO-HD: STATISTICAL ANALYSIS PLAN

(as measured by cUHDRS and its four components). This will be called LifeHD. Modifiable lifestyle factors will be included, namely:

- Sleep;
- Diet;
- Physical activity;
- BMI.

Additionally, the following non-modifiable measures will be included:

- Age group (< 47yrs, 47 53yrs, > 53yrs);
- CAG repeat length;
- HD stage.

To achieve the scoring sums (LifeHD scores), the steps in Appendix C will be followed.

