Appendix C: LifeHD score

Table 4 reports the covariates which will be included in the LifeHD index. The following algorithm describes the development of the score.

- Step 1. The risk factors will first be included separately in a regression model (together with non-lifestyle factors: age, sex, HD stage, time since diagnosis, and follow-up time since last visit). We will use a linear or logistic regression model, depending on the outcome (continuous or binary). This will also enable us to understand the impact of each category on the outcome variable and define the reference category for each factor. For diet, the sign and magnitude of each category will allow us to understand the most and least beneficial clusters thus the beneficial category is group 1, and the other category is 0. The least beneficial cluster will be the reference category to another (group 1 or higher for more than two categories) will increase the index thus, higher values of the index indicate "better" lifestyle.
- Step 2. Factors that were significant in the first step will be simultaneously placed into a single regression model linear or logistic regression depending on the outcome. (For DOMINO-HD, as the outcome is cUHDRS or its components linear regression will be used.)
- Step 3. From the final regression models of step 2, risk scores will be assigned for each factor with the respective β coefficients (steps 4 and 5).
- Step 4. All β coefficients will be standardised so that the lowest one has a value of 1 this is achieved by multiplying every β coefficient with 1/minimum(β).

TPL/008/2(v1.0)

DOMINO-HD: STATISTICAL ANALYSIS PLAN

Step 4b.	(optional) Rounding each coefficient to the closest integer. In this case,
	all individual scores are positive integers. This will enable easier
	calculaiton of the scores, and higher values of the score would indicate
	better "lifestyle".

Step 5. The risk score for an individual will be obtained by summing the scores for the appropriate level of each of the risk factors.

Correlation and association of LifeHD with the outcome and the lifestyle factors under study (diet, sleep, physical activity) will be tabulated.

Variable	Calibration
Diet*	MDI: 0-5; 6-9
	HEI: 0-59; 60-100
Sleep*	SE > tertile/quantile
	$SE \leq tertile/quantile$
Physical activity*	MET > tertile
	$MET \leq tertile$
BMI*	$BMI \le 25 \text{ normal}$
	$25 < BMI \le 30$ overweight
	BMI > 30 obese
Age**	< 47 years old
	47 – 53 years old
	\geq 53 years old

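### The SAP says LifeHD will include sleep, diet, physical activity and BMI, but Appendix C Step 2 keeps only factors significant in Step 1 and names no adjusters, so lifestyle factors can drop out

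*SAP*

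**What the plan says.** SAP section 6.2 (construction of the LifeHD score) fixes the content of the index: "Modifiable lifestyle factors will be included, namely" sleep, diet, physical activity and BMI. It adds age group, CAG repeat length and HD stage as non-modifiable measures. Appendix C opens in the same way: "Table 4 reports the covariates which will be included in the LifeHD index". Neither statement is conditional.

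The algorithm in Appendix C is conditional. Step 1 fits each risk factor in its own model, "together with non-lifestyle factors: age, sex, HD stage, time since diagnosis, and follow-up time since last visit". Step 2 reads: "Factors that were significant in the first step will be simultaneously placed into a single regression model". Step 3 takes the weights from that model: "From the final regression models of step 2, risk scores will be assigned for each factor with the respective β coefficients". Step 4 multiplies every coefficient by the reciprocal of the smallest one, and Step 5 sums the results.

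Table 5 interprets a higher LifeHD as a better overall lifestyle and names diet, sleep and physical activity. Section 6.2.2 uses LifeHD as the treatment variable, once with the three lifestyle factors as confounders and once alone.

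**The concern.** The stated content and the algorithm cannot both hold unless every listed factor passes its Step 1 test. The SAP does not say whether a non-significant lifestyle factor is kept, or what LifeHD is if none passes.

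Three things are at stake.

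- **Meaning of the index.** HD stages 1 to 3 are defined by TFC, and TFC is a component of cUHDRS, so stage is very likely to pass the screen. Modest lifestyle effects may not. LifeHD could then consist largely of stage, age and CAG under a lifestyle label.
- **Comparability.** LifeHD is studied against cUHDRS and its four components. If the screen is run for each outcome, up to five differently composed indices could share one name.
- **The weights.** They come from Step 2, and Step 2 names none of the five variables that Step 1 adjusts for.

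**Working it through.** **Inputs.** Significance level: "All p-values will be compared to 5% level of significance" (section 4.1), taken as two-sided because sidedness is not stated. Multiplicity adjustment: "None due to the exploratory nature of the study" (section 4.1.1). Planned N: 300 to 450 (section 3.3). Follow-up at 12 months counts as feasible above 70% (section 6.1.1), which is 0.70 × 300 = 210 at that boundary. Sleep (section 6.2) and MET-minutes (Table 4) are cut at a tertile, about 1:2.

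**The plan's own figure.** Section 3.3 states "we will have 80% power to detect effect sizes that are at least as large as 0.23 for each environmental measure", for continuous predictors at N = 300. For a standardised slope, the minimum detectable effect is (1.960 + 0.842)/√(N/DE), where DE is the design effect of the weighting.

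- DE = 1: 2.802/√300 = 0.162.
- DE = 2: 2.802/√150 = 0.229.
- Solving for 0.23: effective N = (2.802/0.23)² = 148, so DE = 300/148 = 2.02.

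The SAP gives no DE. The figure is consistent with a DE near 2 but cannot be confirmed.

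**Survival at the plan's 80% power per factor** (independent selection assumed).

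- All three of sleep, diet and activity: 0.8³ = 0.51.
- All four modifiable factors: 0.8⁴ = 0.41.
- None of four: 0.2⁴ = 0.002.
- Expected number kept: 4 × 0.8 = 3.2.

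**Survival as binary factors.** Power = Φ(d/√(1/n₁ + 1/n₂) − 1.960), with n₁ = N/3 and n₂ = 2N/3. The SAP gives no binary effect size, so d is an assumption with two readings:

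- 0.23 is itself the difference between the two groups: d = 0.23.
- 0.23 is per SD of a normally distributed predictor. A tertile cut separates the group means of the predictor by 0.545 + 1.091 = 1.636 SD, so d = 0.23 × 1.636 = 0.376.

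At N = 300 the standard error is √(1/100 + 1/200) = 0.1225. This gives Φ(1.878 − 1.960) = 0.47 and Φ(3.073 − 1.960) = 0.87.

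| d | N | One factor | All three | All four | None of four |
|---|---|---|---|---|---|
| 0.23 | 210 | 0.35 | 0.04 | 0.015 | 0.18 |
| 0.23 | 300 | 0.47 | 0.10 | 0.05 | 0.08 |
| 0.23 | 450 | 0.63 | 0.25 | 0.16 | 0.02 |
| 0.376 | 210 | 0.73 | 0.39 | 0.28 | 0.005 |
| 0.376 | 300 | 0.87 | 0.65 | 0.57 | <0.001 |
| 0.376 | 450 | 0.96 | 0.90 | 0.86 | <0.001 |

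Outside this range at N = 300: at d = 0.10, none of four survives in 0.58; at d = 0.50, all four survive in 0.93. With no effect at all, none survives in 0.95⁴ = 0.81.

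**Adjusters, step by step.**

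| Variable | Step 1 | Step 2 as written |
|---|---|---|
| Age, HD stage | Always | Only if selected as index factors |
| Sex, time since diagnosis, follow-up time | Always | Not named, and not in Table 4 |

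A simulation with assumed inputs shows the direction of the effect (N = 300, 2000 runs). Time since diagnosis worsened the outcome and went with poorer lifestyle, and the true lifestyle effects were zero. Among retained factors, the mean lifestyle coefficient was 0.28 with no adjusters, 0.12 with age and stage only, and −0.01 with age, sex, stage and time since diagnosis. Follow-up time was not simulated. These values illustrate a mechanism and do not estimate the bias in this study.

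**The case against.** The study is declared exploratory, its primary objective is feasibility, and section 6.2.1 analyses each lifestyle factor separately whatever LifeHD contains. All of this stands and limits the consequence to a secondary index.

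A reader might infer that LifeHD will rarely hold the lifestyle factors because effects of the planned size would mostly fail Step 1. The SAP does not support that. Its 0.23 is for continuous predictors; read per SD with a tertile cut, each factor passes with probability 0.87 at N = 300. Even at a binary 0.23 SD, about 4 × 0.47 = 1.9 of four factors are expected to stay. The 1:2 split is also an assumption for diet, which is cut at fixed MDI or HEI scores with no expected proportions, and for BMI, which has three levels.

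A reader might also infer that the weights are unadjusted for stage and age and so heavily biased. Suppose activity falls evenly from 85% to 40% over four equal stages, and stage shifts the outcome by 0.4 to 0.8 residual SD per step. A null activity factor would then take a coefficient of about 0.29 to 0.48 SD, but only with stage absent from Step 2. Stage is itself an index factor. Its test statistic in that setting is at least about 0.4 × 1.118 × √300 = 7.7, so it would be selected, and its presence removes this bias. The clear gap is sex, time since diagnosis and follow-up time.

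Nor does Step 1 test factors unadjusted: each enters with five non-lifestyle variables. One could assume that these carry over to Step 2, but the text does not say so.

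**Conclusion.** The point holds as a contradiction in the SAP that needs no calculation: an unconditional content list against a significance filter, with no rule for a factor that drops out. Losing at least one of the four modifiable factors has probability 1 − 0.41 = 0.59 even at 80% power per factor. At N = 300, all three of sleep, diet and activity survive in about 10% to 65% for an assumed 0.23 to 0.38 SD. These figures assume independent selection, equal effects and, for the binary case, a 1:2 split. The supported statement is that LifeHD may omit one or more lifestyle factors and could hold none if effects are small.

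The missing adjusters are a second, narrower gap. The weights can be confounded by the three variables named only in Step 1, and by age or stage if either is not selected. The SAP does not allow the size of this to be estimated. The algorithm should be corrected before the index is built; the feasibility outcomes are unaffected.

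**What to change.** - Delete the significance screen. Enter all factors listed in section 6.2 together in the Step 2 model, and report the separate Step 1 models descriptively.
- Keep all Step 1 adjusters in Step 2. Age and HD stage are then always present; sex, time since diagnosis and follow-up time are added as adjusters that carry no score.
- Replace the 1/minimum(β) scaling in Step 4. With weak factors kept, the smallest coefficient may be near zero or negative, and the other scores would then become very large or change sign. Using the β coefficients directly, or dividing by a fixed, pre-named reference coefficient, avoids this. The optional rounding in Step 4b and its claim of positive integer scores need the same revision.
- Make the content lists agree: Table 4 also lists antidepressant medication as modifiable, and section 6.2 does not.

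Shrinkage of the coefficients is optional. If the sponsor prefers to keep the screen, the minimum is to say in section 6.2, Appendix C and Table 5 that LifeHD holds only selected factors, to name the Step 2 adjusters, and to state what happens if no lifestyle factor is selected.

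The cost is SAP wording and no new data. The downside is that some weights will be small and imprecise, which should be shown with their confidence intervals.

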6.2.2 COVARIATE ADJUSTMENT

Unweighted analyses (using regression models) will control for age, HD stage, as well as baseline values for the outcomes. Additionally, we will control for the two lifestyle (the continuous version of these) factors not included in each case.

The primary goal is to control for confounding bias, using PS and balancing weights (Markoulidakis, Taiyari, et al., 2021), for the two lifestyle factors other than the one under study in each case. Expecting limitations due to the restricted sample size (Markoulidakis, Holmans, et al., 2021), we will attempt to balance additionally for age, HD stage, and baseline values of the outcome.

The outcome analysis will also be performed using the LifeHD score constructed, as a categorical covariate, with and without the use of PS and balancing weights. The LifeHD score will be used both in addition to the individual lifestyle factors (e.g. using LifeHD score as 'treatment', and the three lifestyle factors as confounders), and solely – without taking into consideration the other lifestyle factors.

Outcome will be standardised, so that we report standardised effect sizes. The estimand of interest (e.g. ATE or ATT) will be determined based on whether adequate balance is achieved or not. If we are unable to achieve adequate balance, then unweighted regression and means difference will be reported.

Additionally, significance tests for difference of means of the covariates we wish to control for and the outcome will be reported. The pseudo-groups will be created using the binary indicators of diet, sleep, and physical activity.

Genetic information (via polygenic risk scores) will only be used in the analysis if it is feasible based on the available sample.

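### LifeHD takes its factors, directions and weights from the study outcome and is then assessed against that outcome in the same participants, so its p-values, intervals and effect sizes are invalid and favour the score

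*SAP*

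**What the plan says.** Section 6.2 states the purpose of LifeHD: the index "will be created to investigate the association of a lifestyle-based score with the progression of HD", measured by cUHDRS and its four components.

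Appendix C gives the algorithm:

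- **Step 1** fits each candidate factor separately ("together with non-lifestyle factors: age, sex, HD stage, time since diagnosis, and follow-up time since last visit") and uses the result to "define the reference category for each factor". Baseline cUHDRS is not among the listed covariates.
- **Step 2** keeps only the factors that were significant in Step 1 and fits them jointly. It names the outcome as cUHDRS or its components.
- **Steps 3 and 4** set the weights: "From the final regression models of step 2, risk scores will be assigned for each factor with the respective β coefficients", rescaled by one over the smallest coefficient.
- **Step 5** sums the points for each participant.

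The finished score is used twice. Section 6.2.2: "The outcome analysis will also be performed using the LifeHD score constructed", as a categorical covariate, with and without weighting. Appendix C: "Correlation and association of LifeHD with the outcome and the lifestyle factors under study" are to be tabulated. The unweighted models of section 6.2.2 adjust for age, HD stage and the baseline outcome.

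On inference, section 4.1 says: "All p-values will be compared to 5% level of significance", alongside 95% confidence intervals. Section 6.2.2 asks for standardised effect sizes. Section 4.1.1 waives multiplicity adjustment because the study is exploratory.

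**The concern.** The score is in effect a fitted value from the outcome regression. Regressing the outcome on its own fitted value in the same people does not test whether lifestyle relates to progression. Part of the association is put there by the construction, and the usual standard error ignores the selection and estimation that came before. The SAP mentions no hold-out sample, cross-validation, optimism correction, externally fixed weights or second cohort.

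Direction is also at stake. Table 5 defines a higher LifeHD as better diet, sleep and activity, but Step 1 lets the data choose the rewarded level. If a binary factor has no true effect, the sign of its coefficient is a coin toss. A retained null factor is then as likely as not to reward the less healthy level, against the score's stated meaning.

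**Working it through.** **The plan's own figure.** The SAP gives no power or error figure for LifeHD. Section 3.3 gives 0.23 as the detectable effect per environmental measure at N = 300. The minimum detectable effect is (1.960 + 0.842) × √(D/300), where D is the design effect from weighting. This is 0.162 at D = 1 and 0.23 at D ≈ 2.02. The figure is consistent with a conservative weighting allowance, is not disputed, and does not bear on this point.

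**Inputs.** From the SAP: N = 300, the 5% level, Steps 1-5, and the section 6.2.2 covariates. Assumed, because the SAP does not give them: factor prevalences, independence of the factors, and a residual correlation ρ between baseline and 12-month outcome of 0.5, 0.7 or 0.9. The true lifestyle effect is set to zero. LifeHD is tested as a continuous score.

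**1. How often a score arises by chance.** With k independent null factors each tested at 5%, the probability is 1 − 0.95^k.
- k = 4: 1 − 0.95⁴ = 18.5%; simulated about 16-18%.
- k = 5: 1 − 0.95⁵ = 22.6%; simulated about 23%.

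**2. Same covariates in building and testing.** If one binary factor is retained, the score is a rescaling of that factor. The final test then repeats the Step 1 test, which was significant by construction. Simulation with four binary factors gives about 100% rejection given a score. A second simulation used five candidates (three-level BMI and antidepressant use included) and a testing model that dropped some Step 1 covariates. It gave 93-94%.

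**3. Baseline outcome in the final model only.** This is the literal reading of Appendix C beside the unweighted model of section 6.2.2. For one retained factor, the Step 1 and final z-statistics correlate at √(1 − ρ²). The closed form is P(|z₂| > 1.96 given |z₁| > 1.96).

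| ρ | √(1 − ρ²) | Closed form, one factor | Simulated, four factors | Simulated, five candidates |
|---|---|---|---|---|
| 0.5 | 0.866 | 53% | 58% | 63% |
| 0.7 | 0.714 | 34% | 36% | 40% |
| 0.9 | 0.436 | 15% | 12% | 17% |

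All exceed 5%.

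**4. Over all studies.** Suppose no score counts as non-significant, and take 17% as the chance of a score. The rates are 0.17 × 58% ≈ 10%, 0.17 × 36% ≈ 6% and 0.17 × 12% ≈ 2%. With matched models the overall rate is about 16-18%.

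**5. Spurious effect size.** For one factor retained at 5%, the mean of |z| is 2.338, so the apparent effect is 2.338/√300 ≈ 0.135 residual SD per SD of score. The five-candidate simulation gave about 0.15 without baseline adjustment; the truth is 0. A real effect is also overstated. With a true 0.10 SD per factor and matched models, the apparent effect was 0.155 against 0.043 in new participants.

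**6. If all factors are kept.** Section 6.2 and Table 4 can be read as including every listed factor. With five candidates and ρ = 0.9, rejection was 70% without baseline adjustment, 17% with baseline in the final model only, and 67% with it in both. Dropping selection does not cure the problem.

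**7. Smaller sample.** At the 70% follow-up threshold of section 6.1.1, N = 0.70 × 300 = 210. With selection, five candidates and no baseline in Step 1, rejection given a score was 92-94% without baseline adjustment and 16-59% with it in the final model only.

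**8. After separating derivation from testing.** Deriving the score in one half and testing it in the other gave 3.3-6.2% rejection and a mean effect between −0.004 and 0.006. A leave-one-fold-out check gave one-sided rejection near 5%.

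**The case against.** **Step 1 does not name the 12-month time point.** This is correct. It is inferred from section 6.1.5 and the stated interest in progression, while Table 5 lists LifeHD as measured at baseline. Building on baseline cUHDRS would weaken the reuse, but the SAP does not say this is intended.

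**The study is exploratory and its primary objective is feasibility.** This bears on severity, and it stands there. It does not make the inference valid: section 4.1.1 uses the word only to waive multiplicity adjustment, and p-values, intervals and standardised effects are still to be reported.

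**The planned outcome model adjusts for baseline, which removes much of the inflation.** This also stands. A reader might infer that LifeHD will be found significant whether or not lifestyle matters, or that the overall false-positive rate is always near one in five. Neither is supported. Under the null most studies build no purely lifestyle score, and with baseline in the final model only the overall rate is about 10%, 6% or 2%. What remains is that any LifeHD result actually reported under selection carries a test well above 5%.

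**The simulated score is not the whole index.** Age group, CAG and HD stage also belong to LifeHD. When they were allowed to enter as assumed prognostic components, the unadjusted association was significant in 100% of simulated studies with no lifestyle effect. That association is partly real, but it is not a lifestyle effect.

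A reader might also infer that an inflated LifeHD coefficient will feed later prediction models. Section 2.1 says only that the data will inform such work; no LifeHD coefficient is carried forward.

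**Conclusion.** The point holds. As written, the naive p-values, 95% intervals and standardised effects for LifeHD are invalid and biased towards the score. Given that a score exists and no lifestyle effect does, the chance of significance runs from about 12% to about 100%, against a nominal 5%. The covariate sets used in building and testing, and the baseline-to-12-month correlation, determine where in that range it falls.

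The figures rest on assumed prevalences, independent factors and assumed correlations, and cover the lifestyle components only. The propensity-weighted and categorical versions, and the version with the three lifestyle factors as confounders, were not simulated. Weighting by itself does not undo the reuse of the outcome.

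The primary feasibility results and the separate sleep, diet and physical activity estimates do not depend on LifeHD. Because LifeHD is a secondary, exploratory analysis, this should be fixed but does not undermine the study.

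**What to change.** **Appendix C**
- Fix the healthy level of each lifestyle factor before outcomes are seen, consistent with Table 5.
- State the time point of the outcome used in Steps 1 and 2.
- Use the same covariates, including baseline outcome, in the building and testing models. On its own this would leave in-sample rejection near 100%, so it must go with the next change.

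**Section 6.2.2**
- Base any LifeHD p-value, interval or effect size on out-of-sample scores. One option is to derive the score in four sites, score the fifth, and rotate.
- Pool the folds on a common scale, because the Step 4 divisor differs by fold. Use the unscaled sums of Step 2 coefficients or scores standardised within fold, and give a score of zero where no factor is retained.
- Take the p-value from a permutation that repeats every step. Alternatively, report a bootstrap optimism-corrected estimate.
- Label the in-sample association, including the Appendix C tabulation, as apparent and give it no p-value.

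**Cost.** SAP wording and some extra R code; no new data. The LifeHD estimate will be smaller and less precise, and with about 240 of 300 participants in each derivation set, folds may retain different factors or none.

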6.1.3 LIST OF SECONDARY OUTCOMES

We will use a clinical composite score for the initial secondary analyses, namely the composite Unified Huntington's Disease Rating Scale (cUHDRS) defined by (Schobel et al., 2017) as follows:

$$cUHDRS = \frac{TFC - 10.4}{1.9} - \frac{TMS - 29.7}{14.9} + \frac{SDMT - 28.4}{11.3} + \frac{SWRT - 66.1}{20.1} + 10$$

where:

- Total Functional Capacity (TFC) is a standard assessment of overall function in HD and ranges from 13 (normal function) to 0 (complete loss of function).
- The Total Motor Score (TMS) has a maximum score of 124. Higher values indicate more severe impairment.
- SDMT is the Symbol Digit Modality Test. Higher scores reflect better cognitive functioning.
- SWRT is the Stroop Word Reading Test. Higher scores reflect better cognitive functioning.

The higher the value of cUHDRS, the better the condition of the patient (lower severity). As the disease progresses and the condition of the individual becomes more severe, the cUHDRS drops.

Individual components of cUDHRS (namely TFC, TMS, SDMT and SWRT) will also explored. This means that the entire analysis described below for the cUHDRS as an outcome will be reproduced for each of the four cUHDRS components (one at a time).

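### LifeHD scaling in Appendix C Step 4 gives the stated score properties only if every Step 2 coefficient is positive, and no step ensures that

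*SAP*

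**What the plan says.** The algorithm is in SAP Appendix C (LifeHD score).

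- **Step 1** fits each factor separately, with non-lifestyle covariates, and uses the result to choose reference categories: "The least beneficial cluster will be the reference category". Moving away from the reference is meant to raise the index.
- **Step 2** puts the factors significant in Step 1 into one joint linear model. It names cUHDRS or its components as the outcome. Section 6.2 likewise describes progression "as measured by cUHDRS and its four components".
- **Step 3** takes the scoring coefficients from the joint model.
- **Step 4** states that the β "coefficients will be standardised so that the lowest one has a value of 1 this is achieved by multiplying every" β by 1/minimum(β).
- **Step 4b**, marked optional, is "Rounding each coefficient to the closest integer. In this case", according to the plan, "all individual scores are positive integers", and higher scores indicate a better lifestyle.
- **Step 5** sums the points.

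On outcome direction, section 6.1.3 says of TMS: "Higher values indicate more severe impairment". It says the opposite of cUHDRS and of the two cognitive tests, and TFC runs from 0 (complete loss) to 13 (normal). Table 5 repeats these directions and defines a higher LifeHD as a better overall lifestyle.

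**The concern.** Step 4 divides by a signed minimum. That suits a set of coefficients that are all positive, but two features of the plan allow negative ones.

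First, the sign of each factor is settled in the separate Step 1 models, while the scored coefficients come from the joint Step 2 model. Signs are not checked again. The lifestyle factors are expected to be related, since sections 6.2.1 and 6.2.2 treat each as a confounder of the others. BMI, age and HD stage also have more than two levels, so each contributes several coefficients.

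Second, TMS runs opposite to the other outcomes and no step reorients it. With the least beneficial category as reference, its beneficial categories have negative coefficients by construction.

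Section 6.2.2 uses LifeHD as a treatment variable in the outcome analysis, with and without weights. A score pointing the wrong way, or one that has lost factors through rounding, would carry into those estimates and their interpretation.

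**Working it through.** **Inputs.** The scaling rule, reference rule and outcomes come from Appendix C; outcome directions come from section 6.1.3 and Table 5. The SAP gives no coefficients, so every β below is assumed. The sign results do not depend on these values; the extent of rounding loss does.

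**General form.** Let m = min(β). The points for factor j are β_j/m, and a participant's total is S = (1/m) × Σ β_j x_j, where x_j is 1 if the category applies and 0 otherwise.

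- *Higher is better.* Predicted benefit is B = Σ β_j x_j, so S = B/m. If m > 0, S rises with B. If m < 0, S falls as B rises, for every participant.
- *TMS.* Predicted benefit is B = -Σ β_j x_j, so S = -B/m. With m < 0 this is B/|m|, a positive multiple of benefit.

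**Case 1: all positive, higher is better.** β = 0.2, 0.3, 0.5, 0.8 and m = 0.2 give 1, 1.5, 2.5, 4. The rule works as the plan describes.

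**Case 2: one negative, higher is better.** β = 0.5, 0.2, -0.1 and m = -0.1:
- 0.5/(-0.1) = -5
- 0.2/(-0.1) = -2
- (-0.1)/(-0.1) = +1

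| Profile | Predicted benefit | LifeHD |
|---|---|---|
| first two factors only | 0.5 + 0.2 = 0.7 | -5 - 2 = -7 |
| none | 0 | 0 |
| third factor only | -0.1 | +1 |

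The best predicted profile gets the lowest score, and two of the three point values are negative. A four-factor example behaves the same way: -0.1, 0.3, 0.5, 0.8 gives 1, -3, -5, -8, and over all 0/1 profiles the correlation of score with predicted benefit is -1.00.

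**Case 3: TMS, all negative.** β = -1, -1.5, -2.5, -4 and m = -4 (the strongest factor):
- unrounded: 0.25, 0.375, 0.625, 1. The ratios 1 : 1.5 : 2.5 : 4 are kept, and the correlation with benefit is +1.00.
- after Step 4b: 0, 0, 1, 1. Two of four factors contribute nothing, only three distinct totals remain (0, 1, 2), and the correlation falls to 0.91.

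In general, when all TMS coefficients are negative the rounded points are 0 whenever |β_j|/max|β| is below 0.5. The loss depends on the spread: -2.2, -2.5, -3, -4 gives 0.55, 0.625, 0.75, 1, which rounds to 1, 1, 1, 1 (correlation 0.97). No factor is lost there, but all differences in weight are.

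**Could recoding make the TMS coefficients positive?** Only by taking the most beneficial category as reference. That contradicts Step 1, and a higher score would then mean a worse lifestyle.

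**Check of the fix.**
- *TMS.* With -TMS, Case 3 becomes 1, 1.5, 2.5, 4, or 1, 2, 3, 4 with halves rounded up (correlation 0.994).
- *Higher is better.* Dividing Case 2 by the smallest absolute value, 0.1, gives 5, 2, -1. Direction is restored, but one score is still negative, so a rule for that factor is also needed.
- *Rounding.* After division by the smallest |β|, every point has absolute value at least 1, so none can round to 0.

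**The case against.** **The intended sign is positive.** Step 1 chooses references so that effects run in the beneficial direction, it already adjusts for several covariates, and only factors significant there reach Step 2. Reversal therefore needs a factor to change sign between the separate and joint models. This stands as a limit on likelihood: the SAP supplies no basis for a probability, and none is claimed here. It does not remove the gap, because nothing in Steps 2 to 4 checks for the change.

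**A reversal would be noticed.** Appendix C tabulates the correlation of LifeHD with the outcome and the lifestyle factors, which would expose a fully reversed score. But the plan gives no rule for what follows, so the repair would be made after seeing the results.

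**Stronger readings that the document does not support.**
- A reader might infer that any negative coefficient reverses or collapses the score, TMS included. It does not: all-negative TMS coefficients, left unrounded, keep direction, ranking and relative weights. Loss of factors arises only through Step 4b, which is optional.
- A reader might say that the lowest coefficient fails to become 1. Dividing by the algebraic minimum always gives that coefficient the value 1; for TMS it is simply the strongest factor.
- A reader might object that a positive minimum near zero inflates the other points. That multiplies the whole score by a common constant and changes no ranking, relative weight or correlation.

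**LifeHD is not primary.** Section 6.1.1 bases the primary outcome on feasibility criteria, and LifeHD is not among them. Section 4.1.1 calls the study exploratory. This stands and limits the severity.

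**Conclusion.** The rule is wrong as written and should be fixed. Step 4 presumes that all Step 2 coefficients are positive, and no step makes them so.

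- For cUHDRS, TFC, SDMT and SWRT, a single negative retained coefficient reverses the entire score. This is exact algebra; only its likelihood is unknown.
- For TMS, negative coefficients follow from the plan's own reference rule. The harm is confined to the optional rounding, where any factor less than half as strong as the strongest scores 0 and the positive-integer statement fails.

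The coefficient values are assumed. The conclusion also takes Step 1's reference rule, worded around diet, to apply to every factor, and Step 2's mention of the components to mean that the algorithm is run on TMS as well. No primary feasibility result depends on Step 4, so this is not a must-fix point.

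**What to change.** Revise Appendix C as follows:

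1. Before Step 1, orient every outcome so that higher is better, using -TMS in place of TMS.
2. In Step 4, divide by the smallest absolute value among the retained Step 2 coefficients and keep each sign. Alternatively, use the unscaled β.
3. Between Steps 2 and 4, state that a factor whose sign reverses in the joint model is re-referenced (for a multi-level factor, to its least beneficial level in that model) or removed and the model refitted, and say which of the two applies.
4. Keep the positive-integer statement in Step 4b only if items 1 to 3 are adopted with scaling by the smallest absolute coefficient. Otherwise delete it.

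The cost is one paragraph in Appendix C and a few lines of code. No further data are needed. It should be settled before the joint models are fitted, so that the handling of a sign change is not chosen with the results in view.
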